### **Proposed Study**

This study will be implemented as a pilot study to test the use feasibility of the iThermonitor as a clinical decision support for continuous temperature monitoring in a dyad of 25 pediatrics patients, (aged 2yrs – 17yrs) on myelosuppressive therapies for acute leukemia and other childhood cancers at the MGH Pediatric Hematology and Oncology group and their caregivers. The iThermonitor will be used by patients and their caregivers for 14 days of data collection. There will be up to be two study visits: study enrollment and study closeout. Participants will be given the option to complete study closeout online via RedCap. REDCap is a secure, web-based application for building and managing on line surveys. The REDCap version offers a more convenient means for survey administration and eliminates the need for an in-person closeout visit. Should the participant choose this option, a member of the study staff will email a link to the RedCap survey via RedCap's secure email system.

We have chosen to implement this study as a feasibility study because our goal is to determine if continuous temperature monitoring by the iThermonitor can work in home settings. This is in keeping with the definition for feasibility studies proposed by the National Institute for Health Research Evaluation, Trials and Studies Coordinating Centre (NETSCC), which states that "feasibility studies are pieces of research done before a main study in order to answer the question 'can it work?'" Bowen et al further suggests that they could be used to answer the questions – "does it work and will it work?" and that they are used to determine whether an intervention is appropriate for further testing. Based on the paper by Bowen et al describing the diverse types of feasibility studies funded by the National Cancer Institute, this study meets the criteria for conducting feasibility studies. According to them, one of the indications for a feasibility study is when "there are few previously published studies or existing data using a specific intervention technique". To our knowledge, we are not aware of any previous research exploring continuous temperature monitoring in pediatric oncology patients on myelosuppressive therapies. Therefore, findings from this study have the potential to advance knowledge about the management of fever in pediatric patients on myelosuppressive therapies.

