#### 5.7 Adverse Reactions and their Management:

There is minimal chance for adverse effects directly from this study. However, because the iThermonitor is attached to the skin a hydrogel dressing patch, we cannot rule out the possibility of a skin reaction to the adhesive surface of the device. After discharge from the hospital, we will instruct caregivers to continue monitoring patients as recommended by their care providers. While we do not expect the iThermonitor to fail, we will emphasize that caregivers are to continue all standard protocols care for each patient.

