#### 5.72 Anticipated Reactions

We do not anticipate any adverse reaction consequent to participating in this study. This study is not invasive and does not prescribe medications nor recommend new treatment protocols. The iThermonitor only helps to timely detect the onset of out-of-range temperature. Participants will be advised to contact their physicians if they experience any problems with their medications or medical illness

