### 6.1 Primary and secondary endpoints

6.1a Primary outcome measurement: use feasibility of the iThermonitor will be assessed by ability of the device to successfully capture, transmit and display the patient's body temperature data on the study iPad mini. To limit recall bias, subjects will be required to log (Appendix 5) the ability to view the temperature data on the iPad mini once a day for the entire duration of the study. The device will be deemed a feasible continuous temperature monitoring tool if at least 80% of study subjects are able to successfully use the iThermonitor to monitor their body temperature. A subject must be able to view temperature data on the provided iPad mini at least 80% of the time in the study to be considered successful. "Time in the study" here is defined as the number of days the subject spends in the study which is expected to be two weeks.

6.1b Secondary outcomes: secondary outcomes which will be assessed at the end of the study include:

- i. Usability, acceptability and satisfaction with the iThermonitor. This will be assessed by questionnaires specifically designed for this study. We will be assessing ease of use, acceptability, connection and use problems like the device falling off the skin, usefulness of out-of-range temperature alerts and adverse reactions. We will also assess to see if the device helps to build caregiver self-efficacy skills in caring for the patient.
- ii. Caregiver engagement with the iThermonitor. This will be assessed by time to first measurement and upload from the time of discharge and also by the frequency of logins to the iThermonitor app.
- iii. Caregiver anxiety will be assessed using the GAD-7 questionnaire.

6.2 Sample size and statistical power or precision associated with the sample size: The length of time required to accrue an adequate number of subjects to the study should be indicated.

We will be able to estimate a feasibility success rate of 80% to within a 95% confidence interval of +/- 16% with a sample size of 25 evaluable patients. This is in keeping with a

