## Using and maintaining the iThermonitor

- Charge the iPad regularly and keep the iThermonitor app open. Do not log out of the app.
- Make sure the Bluetooth is in the on position.
  - If you have a Wi-Fi connection in your home, connect the iPad to the Wi-Fi to allow the iThermonitor to sync for data collection.
- DO NOT change settings of the iPad or the iThermonitor app.
- DO NOT get the iThermonitor wet (shower, bath swimming, etc).
- DO NOT wear the iThermonitor at one side for more than 24 consecutive hours. Change sides everyday to wear it for continuous monitoring.
- If your child feels unwell (uncomfortable or allergic) when using the patch, replace it with another type of adhesive dressing based on your doctor's advice. A fully-covered patch larger than 76mm×62mm should be used.
- Do not reuse the patches. If a patch is already folded over, a new patch is required.

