**13. What problems did you experience?**  
(Please circle **all that apply**)

- a. Problems keeping the device on my child's body
- b. Problems linking the device with my smartphones
- c. Problems with the iThermonitor battery
- d. Problems setting out-of-range temperature alerts
- e. Other problems: \_\_\_\_\_

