### iThermonitor Daily Event Monitoring Log

Please indicate **Yes** or **No** for each column everyday during the study.

Day	The iThermonitor stayed on the body for most of the day		I was able to view the temperature data on the iPad mini	
	Yes	No	Yes	No
1				
2				
3				
4				
5				
6				
7				
8				
9				
10				
11				
12				
13				
14				

Caregiver Signature \_\_\_\_\_ Date \_\_\_\_\_

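### Section 6.1b(i) promises adverse reactions by questionnaire, but no form shown asks about a skin reaction, so the count is likely too low and a zero would not show good skin tolerability.

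*Combined protocol and SAP*

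**What the plan says.** Section 6.1b(i) sets usability, acceptability and satisfaction as a secondary outcome. On the instrument it says "This will be assessed by questionnaires specifically designed for this study", and the content it lists ends with "use problems like the device falling off the skin, usefulness of out-of-range temperature alerts and adverse reactions". Section 6.7 leaves this outcome to descriptive statistics.

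Section 5.7 names one specific device reaction: "we cannot rule out the possibility of a skin reaction to the adhesive surface of the device". Section 5.72 then says "We do not anticipate any adverse reaction consequent to participating in this study".

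Section 5.71 makes the investigator responsible for documenting every adverse event, including date and time of onset and resolution, intensity and frequency. Section 5.73 describes recording, classifying and reporting an event once it has been encountered, and classifies partly by whether it was anticipated.

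The user manual (Appendix 1.4) tells a caregiver whose child is uncomfortable or allergic with the patch to "replace it with another type of adhesive dressing based on your" doctor's advice. It does not ask the caregiver to inform the study. Close-out may be done online, an option that, in the Proposed Study section, "eliminates the need for an in-person closeout visit".

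**The concern.** The plan names an outcome and an instrument, but the instrument as shown does not contain the question. Spontaneous reports usually fall short of solicited ones, and the shortfall makes the device look better. The children are myelosuppressed and wear an adhesive patch for 14 days, so patch-site tolerability is something later studies would want from this pilot. If few or no reactions are reported, the reader cannot tell whether there were none or nobody asked.

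There is also a dating problem. Section 5.71 wants onset and resolution, and a remark volunteered at two weeks will rarely supply them. The plan uses a daily log for the primary outcome specifically to limit recall bias, but gives reactions no such protection.

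**Working it through.** **Step 1: the plan's own figure.** The only precision statement is plus or minus 16 points for an 80% success rate with 25 evaluable patients (section 6.2). It reproduces: 1.96 × √(0.8 × 0.2 / 25) = 0.157. It concerns the primary endpoint and is not in dispute. The plan gives no figure for adverse reactions.

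**Step 2: the forms against the promise.**

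| Source | What it asks | Skin reaction asked? |
|---|---|---|
| Close-out survey, question 1 | Ratings of ease, caregiver comfort, confidence and alerts; Yes/No on wear and viewing | No |
| Close-out survey, questions 12 and 13 | Any problem using the device; then a list starting with "Problems keeping the device on" and going on to linking, battery, alert setting and an open option (13e) | Only if written in under 13e |
| Close-out survey, questions 14, 15 and 18 | Free text on problems, free text on wished-for additions, offer of an interview | Only if volunteered |
| Daily log | "The iThermonitor stayed on the body for most of the day", and whether data could be viewed | No; a No for wear carries no reason |
| GAD-7, enrollment survey | Anxiety; demographics and technology use | No |
| Assessment table, section 5.4 | No adverse event row | No |
| Sections 5.61 to 5.64 | No step described that asks about reactions; the one follow-up call is triggered by missing device data | No |

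The close-out questions run from 1 to 18 without a gap, so a lost survey question is unlikely.

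**Step 3: what incomplete capture does.** Let r be the true proportion of children with a reaction and s the share of reactions captured by any route, including 5.71 to 5.73. Neither is in the documents; both are assumptions. With independent children and no false reports, P(no report) = (1 − r·s)^25.

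| True rate r | Expected true count, 25r | s = 100% | s = 75% | s = 50% | s = 25% |
|---|---|---|---|---|---|
| 5% | 1.25 | 28% | 38% | 53% | 73% |
| 10% | 2.5 | 7% | 14% | 28% | 53% |
| 20% | 5 | 0.4% | 1.7% | 7% | 28% |

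For example, r = 10% and s = 50% give (1 − 0.05)^25 = 0.28.

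**Step 4: what a zero would mean.** For 0/25 the exact two-sided 95% upper limit is 1 − 0.025^(1/25) = 13.7%. That limit applies to the reported rate r·s. It bounds the true rate only if s = 1. If s were known to be 50%, the bound on r would be 13.7 / 0.5 = 27.4%; at 25% it would be 13.7 / 0.25 = 54.8%. Since s is unknown, no bound can be given.

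**The case against.** Four replies deserve weight.

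First, a reader might infer that adverse reactions cannot be measured at all with these forms. The documents do not support that. Option 13e takes other problems. A No at question 12 skips to question 14, so every respondent reaches that free text, although it refers back to problems already marked. Question 15 is open to all, and question 18 offers everyone a conversation with staff. Removal of a patch would show indirectly in the wear items. These routes exist, but all are unprompted or indirect.

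Second, a reader might infer that nothing anywhere in the study asks about reactions. That also goes too far. The adverse event reporting log is not shown, consent text and parts of the phone script are not available, and the assessment table mentions other close-out surveys. An in-person close-out is planned with online completion as an option, section 5.65 has research assistants administer the questionnaires, and staff are available for troubleshooting. The finding is limited to the forms and steps shown.

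Third, the clash between 5.7 and 5.72 might be read as making classification differ between dyads. That is speculation. Possible but not expected is a coherent position, and 5.72 taken literally makes every reaction unanticipated. What stands is loose wording on a distinction that 5.73 uses.

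Fourth, adverse reactions are one descriptive sub-item. The plan sets no tolerability criterion, so no formal decision would change. That is correct and limits the weight of the point. It does not remove the mismatch between 6.1b(i) and its instrument.

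**Conclusion.** The point holds in limited form. An outcome assigned to questionnaires has no matching structured question on any form shown, for the one local reaction the protocol specifically names. Capture depends on volunteering or on a passive adverse event route, so the count is likely to be too low, and a zero would not be evidence of good skin tolerability.

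The size cannot be fixed from the documents. Over the assumed ranges (true rate 5% to 20%, capture 25% to 100%) the chance of no report runs from 0.4% to 73%. The useful reading is the movement along each row: at a true rate of 10%, falling from full to one-quarter capture raises it from 7% to 53%. The primary endpoint, its analysis and the sample size are not affected.

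**What to change.** - **Close-out survey:** add one Yes/No item on a skin reaction at the patch site, with worst intensity on the mild/moderate/severe scale of 5.71 and start and end day. Place it outside the question 12 skip.
- **Daily log:** add one Yes/No column for a skin reaction that day, so that onset and resolution can be dated as 5.71 requires.
- **User manual:** add a line asking caregivers to tell study staff as well as their doctor.
- **Section 6.7:** report the result as n/N with an exact 95% confidence interval. With 25 children this stays wide even with full capture: 5/25 would give 6.8% to 40.7%, the mirror of 59.3% to 93.2% for 20/25.
- **Minor:** reconcile the wording of 5.7 and 5.72, because 5.73 classifies events by whether they were anticipated.

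The cost is a small amendment to two forms, the manual and the text, plus a few seconds a day for the caregiver. The reported rate of mild reactions will probably rise, and the report should say that they were solicited. The log column has to be in place before use, because daily answers not asked for cannot be recovered.

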#### ***Registration Process for DF/HCC and DF/PCC Institutions***

The QACT registration staff is accessible on Monday through Friday, from 8:00 AM to 5:00 PM Eastern Standard Time.

The registration procedures are as follows:

- Obtain written informed consent from the participant prior to the performance of any protocol specific procedures or assessments.
- Complete the QACT protocol-specific eligibility checklist using the eligibility assessment documented in the participant's medical record and/or research chart. **To be eligible for registration to the protocol, the participant must meet all inclusion and exclusion criterion as described in the protocol and reflected on the eligibility checklist.**
- Fax the eligibility checklist(s) and all pages of the consent form(s) to the QACT at [contact]. For Phase I protocols, attach participant dose level assignment confirmation from the sponsor.
- The QACT Registrar will (a) review the eligibility checklist, (b) register the participant on the protocol, and (c) randomize the participant when applicable.
- An email confirmation of the registration and/or randomization will be sent to the Overall PI, study coordinator(s) from the Lead Site, treating investigator and registering person immediately following the registration and/or randomization.

5.63 During the study:

- If the study team does not receive data from the iThermonitor by the second day after study enrollment, study staff will follow-up (telephone call) with subjects to ensure that they are able to correctly set-up the device. We will encourage participants to continue to receive medical treatment and adhere to other management protocols as recommended by their physicians as usual. We will emphasize that the iThermonitor does not replace usual temperature monitoring protocols.
- Use the iThermonitor everyday to monitor the patient's temperature continuously until final study closeout.
- Complete the event monitoring log every day.
- In the event of a hospital admission during the study period, the hospitalized subject will stop using the device. If the subject has contributed less than 50% of data (i.e. used the device for less than 7 days) prior to hospitalization, they will be dropped from the study and another subject will be recruited to make up the enrollment

target. However, subjects who have contributed at least 50% of data prior to hospitalization will stop using the device but will be included in final analyses.

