### 6.7 Analysis plan

Data collected will be verified before analysis, which will be done with Data Analysis and Statistical Software: STATA, version 13 with an alpha of 0.05 set a priori. All participants will be followed up for two weeks and we will summarize their baseline demographic and technology use characteristics.

To address the primary aim, the feasibility success rate will be calculated as the number of evaluable patients who meet the criteria for 'success' (per section 6.1) divided by the total number of evaluable patients. A 95% confidence interval will be calculated on this proportion. If the upper limit of the 95% confidence interval is less than 80%, then we will consider the iThermonitor not to be a feasible clinical decision support tool.

Descriptive analyses will be performed on all baseline data. Endpoints for all study outcomes are defined in section 6.1 above. All continuous variables will be computed as means with standard deviations, median and ranges while categorical variables will be computed as frequency distributions and percentages. The binomial test of proportion will be used to our dichotomous outcome of successfully using the iThermonitor. Paired t-test will be used to

analyze pre- and post- GAD-7 scores measured as a continuous variable. All other outcome variables will be summarized with descriptive statistics.

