#### 6.8 Handling of missing data in the analysis

We have adopted simple data collection techniques to limit missing data for this trial. Since this is largely exploratory work with descriptive statistics, a complete case analysis approach will be adopted for this study. .

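### The time component of caregiver engagement leaves out dyads that stay home and never start, so time to first use looks shorter than it was

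*Combined protocol and SAP*

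**What the plan says.** Section 6.1b(ii) of the combined protocol and SAP gives caregiver engagement two measures. One is a time: "This will be assessed by time to first measurement and upload from the time of discharge". The other is a count: "and also by the frequency of logins to the iThermonitor app".

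Section 6.7 gives neither measure a method of its own. It states that "All continuous variables will be computed as means with standard deviations, median and ranges" and, for outcomes without a named test, "All other outcome variables will be summarized with descriptive statistics". On follow-up it says "All participants will be followed up for two weeks". On missing data, section 6.8 says "a complete case analysis approach will be adopted for this study". No section sets a censoring day or a time-to-event estimate, or asks for the number of dyads with no first event.

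The drop-and-replace rule in 5.63 and 6.6 covers only subjects admitted to hospital with fewer than 7 days of use. Section 5.63 also provides for a staff prompt: "If the study team does not receive data from the iThermonitor by the second day after study enrollment", staff telephone the family. The user manual (Appendix 1.4) says "If you have a Wi-Fi connection in your home, connect the iPad to the Wi-Fi to allow the iThermonitor to sync for data collection".

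**The concern.** A time to first event does not exist for a dyad in which the event never happens. Under the general rules of 6.7 and 6.8, such a dyad contributes nothing to the mean or median, and on this measure it is the least engaged dyad in the study. The case is foreseeable, because 5.63 plans a call for families whose data do not arrive. A never-starter who stays at home is neither replaced nor given a value.

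The study asks whether monitoring can work at home, and failure to start is part of the answer. A short mean time to first use could be reported with nothing beside it to show how many families it leaves out.

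Two features blur the measure further. A first reading or upload may follow a staff call rather than the family's own initiative. An upload may also come later than first use for reasons unrelated to engagement, because the sensor stores up to 10 days of readings and syncs when a connection returns (5.3, Appendix 1.4).

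**Working it through.** **1. Figures from the plan.** The plan gives no figure for engagement. The sample size is n = 25 (6.2). The precision stated there is for the primary success rate and reproduces: 1.96 × √(0.8 × 0.2 / 25) = 1.96 × 0.08 = 0.157, or ±16%. Only n is used below. The home-use window is 14 days (5.1).

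**2. Assumed inputs.** The documents do not give the number of never-starters, k, or the mean time among starters, m. I take k = 1 to 5 (1/25 = 4% to 5/25 = 20%) and m = 1 to 3 days.

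**3. Mean.** The complete-case mean is m. With never-starters kept and held at day 14, the mean is ((n − k)·m + 14k)/n, so the understatement is k(14 − m)/n. This is a floor, because a never-starter's time lies beyond day 14.

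Example, m = 2 and k = 3: (22 × 2 + 3 × 14)/25 = 86/25 = 3.44 days, against 2.0 reported.

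| Starters' mean (reported) | k = 1 | k = 3 | k = 5 |
|---|---|---|---|
| 1 day | 1.52 | 2.56 | 3.60 |
| 2 days | 2.48 | 3.44 | 4.40 |
| 3 days | 3.44 | 4.32 | 5.20 |

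**4. Median.** With starters' times set at exponential quantiles (an assumed shape, nominal mean 2 days), the complete-case median is 1.39 days. With never-starters kept as censored at day 14, the Kaplan-Meier median is 1.47 (k = 1), 1.68 (k = 3) or 1.96 (k = 5). Leaving never-starters out cannot raise the median, and it moves much less than the mean.

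**5. Share started.** Every complete case has started, by construction. The share among all 25 would be 24/25 = 96% at k = 1 and 20/25 = 80% at k = 5. Those percentages only restate the assumed k.

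**6. Logins.** A non-user has an observable count of zero. At an assumed 2 logins per day among users and k = 3, the mean is 2 × 22/25 = 1.76 with zeros kept and 2.0 if they are dropped. Counting zeros removes the problem.

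**7. Losses in the other direction.** Subjects admitted early are dropped however fast they started (5.63, 6.6), and patients enrolled at a clinic visit have no hospital discharge to count from (4.1). Take 25 assumed times with mean 1.97 and median 1.39, all starters. Losing the 5 fastest raises the mean to 2.41 and the median to 1.84. With one never-starter held at day 14 the mean is 2.22 and the median 1.39. Losing that dyad and the 4 fastest gives 2.04 and 1.64, so the mean falls while the median rises.

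**8. Timing of the staff call.** Inpatients enroll the day before discharge (5.61), and their home use starts the day after discharge (5.1). With enrollment as day 0, discharge is day 1 and the first home day is day 2. Missing data trigger the call by that same second day, so a call can coincide with the start of home use.

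**The case against.** The strongest reply is that the plan never says never-starters are left out. Sections 6.7 and 6.8 are general rules, and nothing bars reporting the number who did not start as a descriptive statistic. Non-start would probably also show elsewhere. A never-starter who completes the daily log fails the primary endpoint, and the close-out survey asks whether and how often the caregiver viewed readings, with never as an option. The staff call also makes never-starting less likely.

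This limits the harm but does not remove the point. The log and survey can be missing for the same families. The exclusion is an inference, but the plan offers no other treatment of a dyad with no time.

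A reader might go further in three ways that the documents do not support:

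- **That engagement as a whole is biased.** It has two measures, and login frequency can score a non-user as zero. It is a weak backstop, though, because the manual tells families to stay logged in.
- **That engagement can only look better than it was.** This is true of never-starters on the time measure. It fails once early-hospitalized dyads and clinic patients without a discharge time are counted (step 7).
- **That upload time measures home internet.** This depends on what upload means. Section 5.4 describes automatic transfer to a paired receiver for cloud storage, and 5.3 makes the receiver link Bluetooth. If upload means reaching the receiver, Wi-Fi is irrelevant; if it means reaching the cloud, the manual makes Wi-Fi relevant. The enrollment questionnaire asks how the caregiver reaches the internet, not whether the home has Wi-Fi, so it would not settle the matter.

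**Conclusion.** The concern holds for the time component of 6.1b(ii). A dyad that stays at home and never starts has no value under 6.7 and 6.8, and its omission lowers the mean and cannot raise the median. For 1 to 5 never-starters and starters' means of 1 to 3 days, the mean is understated by at least 0.44 days (3.44 − 3.0) to 2.60 days (3.60 − 1.0). The central example is 2.0 days against at least 3.44. These sizes rest wholly on assumed inputs. The direction of the never-starter effect does not, but the net direction is open once the other losses are counted.

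The consequence is limited. This is one of two measures of one secondary outcome, summarized descriptively, and it plays no part in the feasibility decision. It is worth correcting because the stated rules produce a misleading summary and a better one is easy to specify.

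**What to change.** In 6.1b(ii) and 6.7:

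- Count time from the scheduled first home day in 5.1: the day after chemotherapy for clinic patients and the day after discharge for inpatients. Section 5.6 instead starts participation the day after the onset of chemotherapy, so the two sections must be reconciled first.
- Report the number and percentage of dyads with a first device-recorded reading by 24 h, 48 h, 7 days and 14 days, or a cumulative-incidence curve. Count never-starters as not reached.
- Censor dyads hospitalized before starting, or show them separately. State how many dyads were dropped and replaced. Because 6.6 removes early-hospitalized dyads, say that they are retained for this summary only; the primary denominator is unchanged.
- Define upload and report first upload separately from first reading.
- Flag first readings that followed a staff call, using the communications kept in the study file (5.5).
- Count zero logins as zero.

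A first recorded reading is the practical event, because no section says how readings on the body are told apart from readings off it.

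The cost is a little more analysis text and an engagement figure that may look less favourable. No new visit or instrument is needed, and the sample size is unchanged; device data are already downloaded weekly (5.4).
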